5.3.2.3 Definition of Disease Progression

Disease progression according to 2008 Modified IWCLL NCI-WG Criteria for Tumor Response is characterized by at least one of the following:

- Appearance of any new lesion, such as enlarged lymph nodes (> 1.5 cm), splenomegaly, hepatomegaly, or other organ infiltrates. An increase by 50% or more in greatest determined diameter of any previous site.
- An increase in the previously noted enlargement of the liver or spleen by 50% or more or the de novo appearance of hepatomegaly or splenomegaly.
- An increase in the number of blood lymphocytes by 50% or more with at least 5,000 B lymphocytes per microliter. The increase should be assessed against the best response while on study.
- Transformation to a more aggressive histology (e.g., Richter's Syndrome). Whenever possible, this diagnosis should be confirmed by lymph node biopsy. For subjects experiencing disease progression due to Richter's Syndrome while on study, supplemental data may be collected.
- Occurrence of cytopenia (neutropenia, anemia or thrombocytopenia) attributable to CLL.

5.3.3 Safety Variables

The following safety evaluations will be performed during the study: serious adverse event and adverse event monitoring including AEs of special interest (Section 6.1.1.4), vital signs, physical examination, and laboratory assessments. Certain types of events require immediate reporting to the Sponsor, as outlined in Section 6.1.6. Safety will be monitored on an ongoing basis and summarized periodically in aggregate safety reports and end of study.

5.4 Removal of Subjects from Therapy or Assessment

5.4.1 Discontinuation of Individual Subjects

Each subject has the right to withdraw from the study and/or study drug treatment at any time. In addition, the Investigator may discontinue a subject from study drug treatment at any time if the investigator considers it necessary for any reason including:

- The investigator believes it is in the best interest of the subject;

- Subject's response to therapy is unsatisfactory, as evidenced by progression of disease while on study drug.
- The subject requires other cancer treatment (e.g., radiotherapy, cancer-related surgery as a result of tumor progression, alternate anti-neoplastic agents) during the study period
- unacceptable toxicity
- The subject becomes pregnant while on the study
- drug/protocol non-compliance

The investigator will inform AbbVie prior to discontinuing a subject from the study by contacting the Clinical Team Leader as identified in Section 7.0. All subjects will be included for analysis of safety data. Subjects who withdraw from the study will not be replaced unless they are not evaluable.

Subjects will continue to be followed for unresolved AEs and survival information for any subject who has not experienced PD at the time of venetoclax discontinuation.

Final Visit

Upon study drug discontinuation and/or upon discontinuation from the study, the reason(s) for discontinuation will be recorded in electronic case report forms (eCRFs) and a final visit will be performed. The final visit procedures as listed in [Appendix D](#) should be performed as soon as possible after discontinuation from study drug.

30-Day Safety Follow-Up Visit

A 30-Day Safety Follow-up Visit should be performed approximately 30 days (\pm 3 days) following the last dose of venetoclax. The 30 day safety follow up procedures listed in [Appendix D](#) should be performed.

Post Treatment and Survival Follow-Up Calls

For subjects who discontinue venetoclax therapy, but do not discontinue the study (), post-treatment follow-up calls will be performed every 6 months (\pm 7 days) for survival

information (i.e., disease progression, the date and cause of death, post-treatment cancer therapies, etc.) and will be collected via telephone calls for a period of 2 years and recorded in the eCRFs.

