After treatment discontinuation, subjects will be followed for disease progression (if progression has not already occurred) and survival. Post-treatment calls will be performed every 6 months until discontinuation from the study. Survival information (i.e., the date and cause of death, post-treatment cancer therapies, date of progression, etc.) will be collected. This period will continue for 2 years following discontinuation of venetoclax.

All study procedures will be performed as outlined in Section 5.3.1.1 and [Appendix D](#) and [Appendix E](#).

For subjects who continue to derive benefit after 2 years of treatment, AbbVie will work with the investigator on a case by case basis to consider the potential continuation of venetoclax therapy. In countries where venetoclax is commercially available, extension of therapy may not be allowed.

A safety analysis will be performed for all subjects participating in the study who took at least one dose of study drug. For the study as a whole, serious adverse events and adverse events will be evaluated and summarized. Laboratory test results and vital signs will be explored for trends and summarized.

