If a subject has an ongoing AE or an unresolved clinically significant laboratory result 30 days following last dose of study drug, the site will attempt to provide follow-up until the AE has resolved to a \leq Grade 1 or baseline or it is the investigator's judgment that the event is unlikely to resolve.

Additionally, CT or MRI scans are not required, however if collected by the site as standard of care, the data should be recorded in EDC.

Post-Treatment and Survival Assessments

After treatment discontinuation, subjects will be followed for disease progression (if progression has not already occurred) and survival. Post-treatment calls will be performed every 6 months until discontinuation from the study. Survival information (i.e., the date and cause of death, post-treatment cancer therapies, date of progression etc.) will be collected. This period will continue for 2 years following discontinuation of venetoclax.

Extended Access Phase

In countries where venetoclax is not commercially available, subjects who continue to derive benefit after 2 years of treatment may be able to extend their treatment for up to 2 additional years. AbbVie will work with the investigator on a case by case basis to consider the potential continuation of venetoclax therapy. The Extended Access Visits will include:

- Collection of Survival information
- AE/SAE/Con Med assessment
- Study drug reconciliation and dispensing

All other procedures should be performed as standard of care. The specific study assessments to be performed during these visits are detailed in Appendix E Study Activities.

Assignment of Subject Numbers

Subjects will be assigned unique consecutive subject numbers at screening, as described in Section 5.5.3. The results of all screening evaluations must be within clinically acceptable limits, upon review by the investigator before a subject can be administered

study drug. Subjects will not be enrolled in the study if laboratory or other screening results are unacceptable.

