6.1.1 Definitions

6.1.1.1 Adverse Event

An adverse event (AE) is defined as any untoward medical occurrence in a subject or clinical investigation subject administered a pharmaceutical product and which does not necessarily have a causal relationship with this treatment. An adverse event can therefore be any unfavorable and unintended sign (including an abnormal laboratory finding), symptom, or disease temporally associated with the use of a medicinal (investigational) product, whether or not the event is considered causally related to the use of the product.

Such an event can result from use of the drug as stipulated in the protocol or labeling, as well as from accidental or intentional overdose, drug abuse, or drug withdrawal. Any worsening of a pre-existing condition or illness is considered an adverse event.

Worsening in severity of a reported adverse event should be reported as a new adverse event. Laboratory abnormalities and changes in vital signs are considered to be adverse events only if they result in discontinuation from the study, necessitate therapeutic medical intervention, meets protocol specific criteria (see Section 6.1.9 Toxicity Management) or if the investigator considers them to be adverse events.

For this protocol, disease progression is an efficacy endpoint. These data will be captured as efficacy assessment data only. Thus, events that are clearly consistent with the expected pattern of progression of the underlying disease (such as transformation to more aggressive histology) will result in discontinuation from the study and should not be recorded as adverse events but reported on the Study Completion eCRF. However, if a subject experiences an adverse event (e.g., pneumonia, pyrexia, fatigue, etc.) and is also found to have disease progression, report the adverse event. If there is any uncertainty as to whether an event is due to disease progression, it should be reported as an adverse event.

An elective surgery/procedure scheduled to occur during a study will not be considered an adverse event if the surgery/procedure is being performed for a pre-existing condition and the surgery/procedure has been pre-planned prior to study entry. However, if the

pre-existing condition deteriorates unexpectedly during the study (e.g., surgery performed earlier than planned), then the deterioration of the condition for which the elective surgery/procedure is being done, will be considered an adverse event.

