6.1.3 Adverse Events Expected Due to Study-Related Endpoints

6.1.3.1 Deaths

For this protocol, overall survival is an efficacy endpoint. Deaths that occur during the protocol-specified adverse event reporting period (Section 6.1.5) that are attributed by the investigator solely to progression of CLL should be recorded ONLY on the Study Completion eCRF. All other on-study deaths, regardless of relationship to study drug, must be recorded on the Adverse Event eCRF and immediately reported to the Sponsor (Section 6.1.5). Death should be considered an outcome and not a distinct event. The event or condition that caused or contributed to the fatal outcome should be recorded as the single medical concept on the Adverse Event eCRF. Generally, only one such event should be reported. The term "sudden death" should be used only for the occurrence of an abrupt and unexpected death due to presumed cardiac causes in a subject with or without preexisting heart disease, within 1 hour after the onset of acute symptoms or, in the case of an unwitnessed death, within 24 hours after the subject was last seen alive and stable. If the cause of death is unknown and cannot be ascertained at the time of reporting, "unexplained death" should be recorded on the Adverse Event eCRF. If the cause of

death later becomes available (e.g., after autopsy), "unexplained death" should be replaced by the established cause of death. During survival follow-up, deaths attributed to progression of CLL should be recorded only on the Survival eCRF.

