Activity	Scr ^a	Within 72 Hours of W1 D1	W1 D1	W1 D2	Within 72 Hours of W2 D1	W2 D1	W2 D2	Within 72 Hours of W3 D1	W3 D1	W3 D2	Within 72 Hours of W4 D1	W4 D1	W4 D2	Within 72 Hours of W5 D1	W5 D1	W5 D2
Informed Consent	X															
17p Deletion or TP53 Mutation	X ^b															
Medical History/Oncology History Assessment	X		X													
Pregnancy Test ^c	X		X													
Adverse Event/Concomitant Medication Assessment	X ^d	X	X	X	X	X	X	X	X	X	X	X	X	X	X	X
Vital Signs	X	X	X	X	X	X	X	X	X	X	X	X	X	X	X	X
Physical Examination ^e	X		X			X			X			X			X	
TLS Risk Assessment ^f	X															
ECOG Performance Status	X		X													
Coagulation Panel	X															
Hematology/Chemistry ^g	X	X ^h	X ⁱ	X ^j	X ^k	X ^l	X ^j	X ^k	X ^l	X ^m	X ^k	X ^l	X ^m	X ^k	X ^l	X ^m
Disease Assessments ⁿ	X															
Contrasted CT or MRI Scan ^o	X															
Bone Marrow Aspirate and Biopsy ^p																
Venetoclax dispensation and accountability ^q			X	X		X	X		X	X		X	X		X	X

Activity	Scr^a	Within 72 Hours of W1 D1	W1 D1	W1 D2	Within 72 Hours of W2 D1	W2 D1	W2 D2	Within 72 Hours of W3 D1	W3 D1	W3 D2	Within 72 Hours of W4 D1	W4 D1	W4 D2	Within 72 Hours of W5 D1	W5 D1	W5 D2
Quality of Life Questionnaires (EORTC QLQ-30, EORTC QLQ-CLL16, EQ-5D-5L) ^f		X	X									X				

Week 8 Through Post-Treatment Follow-Up

Activity	W8 D1	W12 D1	W16 D1	W20 D1	W24 D1	W28 D1	W32 D1	W36 D1	W40 D1	W44 D1	W48 D1	Every 12 Weeks Starting at W60	W108 / Final Visit	30 Day Safety Visit ^s	Post- Treatment Follow-Up ^t
Adverse Event/Concomitant Medication Assessment	X	X	X	X	X	X	X	X	X	X	X	X	X	X	X
Vital Signs*	X	X	X	X	X	X	X	X	X	X	X	X	X	X	
Physical Examination ^{c*}	X	X	X	X	X	X	X	X	X	X	X	X	X	X	
ECOG Performance Status ^u					X						X	X	X	X	
Hematology/Chemistry ^{**}	X	X	X	X	X	X	X	X	X	X	X	X	X	X	
Disease Assessment ^{n*}					X			X			X				
Contrasted CT or MRI Scan ^o											X				
Bone Marrow Aspirate and Biopsy ^p											X				
Venetoclax dispensation and accountability ^{***}	X	X	X	X	X	X	X	X	X	X	X	X	X ^w		
Quality of Life Questionnaires (EORTC QLQ-30, EORTC QLQ-CLL16, EQ-5D-5L) ^f	X	X			X			X			X	X	X		
Collection of Survival Information ^v														X	X

Scr = Screening; W = Wk = Week; D = Day; Post-Treat = Post-Treatment; FV = Final Visit

Study Windows:

* Within 72 hours before or after scheduled visit starting with Week 8 Day 1.

** Within 72 hours prior to scheduled visit starting with Week 8 Day 1.

*** As of Week 8 the visit window for scheduled visits is ± 2 days.

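### Protocol 5.4.1 and 6.1.1.1 conflict with the rest of the protocol on survival follow-up after progression; where sites apply them, the descriptive OS curve can be biased upward

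*Protocol*

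**What the plan says.** **Restrictive wording.**
- Protocol 5.4.1 states that subjects continue to be "followed for unresolved AEs and survival information for any subject who has not experienced PD at the time of venetoclax discontinuation".
- Protocol 6.1.1.1 states that events clearly consistent with progression "will result in discontinuation from the study and should not be recorded as adverse events but reported on the Study Completion eCRF".
- The calls paragraph of 5.4.1 opens "For subjects who discontinue venetoclax therapy, but do not discontinue the study". It carries no progression condition of its own, but it excludes anyone whom 6.1.1.1 has taken out of the study.

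**Unrestricted wording.**
- Protocol 5.1 says that after stopping treatment "subjects will be followed for disease progression (if progression has not already occurred) and survival", for 2 years. The condition in brackets attaches to progression follow-up, not to survival. The synopsis and the Post-Treatment and Survival Assessments text of 5.3.1.1 agree.
- Footnote t of Appendix D and footnote e of Appendix E collect survival information every 6 months for 2 years after study drug is stopped, with no progression limit.
- Protocol 6.1.3.1 presupposes such follow-up: "During survival follow-up, deaths attributed to progression of CLL should be recorded only on the Survival eCRF".

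**Partial cover.** The synopsis, 5.1 and 5.3.1.1 also carry a limit: "Post-treatment calls will be performed every 6 months until discontinuation from the study". They therefore do not fully override 6.1.1.1. Section 5.4.1 adds one later contact for everyone, "A 30-Day Safety Follow-up Visit should be performed approximately 30 days" after the last dose, and the Appendix D row "Collection of Survival Information" is marked at that visit.

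**Analysis.** SAP 10.1.2 counts all deaths, on or off drug, and censors living subjects at the last visit, last contact or date last known alive. OS is reported as a Kaplan-Meier curve and a median with 95% confidence interval. No test is planned.

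**The concern.** For a subject who progresses, a site cannot follow both sets of passages. Under the first set the last survival information would normally come from the 30-day safety visit. Under the second it continues for 2 years.

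A subject dropped at that point is censored about a month after progression. Censoring is then triggered by an event that probably predicts death, whereas Kaplan-Meier assumes that censored subjects have the same later risk as those still followed. If the death rate rises after progression, the deaths removed are disproportionately the ones that should pull the curve down. OS is a named secondary objective, and survival data not collected at the time cannot be fully recovered later.

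**Working it through.** **Step 1: is the conflict in current text?** Yes. All the passages above are in the body or appendices of the current protocol. The amendment rationale in Section 1.1 says that survival is to be followed every 6 months even after progression. The calls paragraph of 5.4.1 now contains an empty bracket, while the no-progression sentence earlier in 5.4.1 and the study-discontinuation statement in 6.1.1.1 remain. The rationale is used here only as evidence of intent.

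**Step 2: inputs.** The documents give no progression rate, death rate or OS target for this study. Their one design figure, 177 subjects, belongs to the primary endpoint: ((1.960 + 1.2816) × 20.5 / 5)² = 176.6, which rounds up to 177. It reproduces and has no bearing here. The following are assumptions, all exponential:
- median time to progression: 24 to 36 months
- median survival after progression: 12 to 36 months
- median time to death without progression: 120 months
- a fraction f of progressors lost 1 month after progression, about the time of the 30-day visit.

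**Step 3: formula.** Let S0 be the share alive without progression, R alive with progression within the last month, and O alive with progression longer ago. Let d and m be the death hazards without and after progression.
- True OS = S0 + R + O.
- Hazard that Kaplan-Meier sees = [d·S0 + m·(R + (1 − f)·O)] / [S0 + R + (1 − f)·O].
- Kaplan-Meier limit = exp(−integral of that hazard).

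If m = d, the observed hazard is d for any f, so the bias is zero.

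**Step 4: one case at Week 48 (11.04 months).** Medians 24, 12 and 120 give hazards 0.0289 for progression, m = 0.0578 and d = 0.0058 per month. Then S0 = exp(−0.0347 × 11.04) = 0.682, R = 0.019 and O = 0.172.
- True death hazard at that time: (0.0058 × 0.682 + 0.0578 × 0.191) / 0.873 = 0.017.
- Hazard seen with f = 0.5: (0.0058 × 0.682 + 0.0578 × 0.105) / 0.787 = 0.013.

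Integrated from zero, true OS is 87.4% and Kaplan-Meier gives 89.7%, an overstatement of 2.3 points.

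**Step 5: all cases, half of progressors lost, progression recognised as soon as it occurs** (true % / Kaplan-Meier % / difference from unrounded values):

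| Medians: progression, survival after it (months) | Week 48 | 2 years |
|---|---|---|
| 24, 12 | 87.4 / 89.7 / +2.3 | 66.7 / 73.7 / +7.0 |
| 24, 24 | 90.7 / 91.8 / +1.1 | 75.9 / 79.8 / +3.9 |
| 24, 36 | 91.9 / 92.6 / +0.7 | 80.0 / 82.5 / +2.5 |
| 36, 12 | 89.4 / 91.0 / +1.6 | 72.4 / 77.9 / +5.5 |
| 36, 24 | 91.6 / 92.5 / +0.8 | 79.0 / 82.1 / +3.1 |
| 36, 36 | 92.5 / 93.0 / +0.5 | 82.0 / 84.0 / +1.9 |

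The worst case, every progressor lost, gives 1.1 to 5.0 points at Week 48 and 4.5 to 17.5 at 2 years.

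**Step 6: recognition only at scheduled assessments.** Disease assessments are scheduled at Weeks 24, 36 and 48, so loss cannot begin as early as Step 5 assumes unless progression is found between visits. Simulating recognition at those visits only, the Week 48 overstatement falls to about 0.3 to 1.2 points with half lost and about 0.6 to 2.7 with all lost. The truth lies between Steps 5 and 6.

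**Step 7: a second set of assumptions.** With 10% death without progression and 20 to 40% progression by 24 months, a death hazard 2 to 10 times higher after progression, and half of progressors lost, the 24-month overstatement is 0.4 to 5.1 points. With a hazard ratio of 1 it is zero.

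**The case against.** The strongest reply is that the sponsor's intent is clear and most of the protocol already carries it out. The rationale for the current amendment says that survival follow-up continues after progression. Section 5.4.1 now lists progression as a reason to stop study drug, not the study. Its headed calls paragraph has no progression condition, and a site working from Appendix D would collect the data. The disputed 5.4.1 sentence is garbled and does not contain the word only. The follow-up call sentence under Disease Assessments in 5.3.1.1 has a similar form and can fairly be read as silent on progressors.

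Most of this stands. It supports treating the two statements as remnants and the severity as minor. It does not remove the conflict: 6.1.1.1 states outright that progression events end study participation, the calls stop at study discontinuation, and nothing says that the appendix prevails over 5.4.1.

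Three stronger readings are tempting but not supported:
- A reader might infer from SAP 6.4 that a lost progressor is counted as alive to the data cutoff. That rule concerns missing death or last-known-alive dates. A lost progressor normally has a last-alive date from the 30-day visit, and SAP 10.1.2 is the specific OS rule. No size is attached to that reading here.
- A reader might infer that the Study Completion eCRF closes a subject out of survival follow-up. Protocol 6.1.3.1 names a separate Survival eCRF, and SAP 10.1.2 lists the survival form separately.
- A reader might take the all-lost figures as expected. They require every site to disregard Appendix D.

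**Conclusion.** The protocol contradicts itself on whether survival is followed after progression, and the restrictive statements are wrong as written. The consequence is conditional: some sites must apply them, and mortality must be higher after progression than before.

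Under the assumed medians, with half of progressors lost, the OS curve is overstated at Week 48 by about 0.3 to 1.2 points if progression is recognised only at scheduled visits and by 0.5 to 2.3 if recognised at once. At 2 years the overstatement is about 2 to 7 points with immediate recognition. The main data cutoff (Protocol 8.1.3) is tied to the last subject's Week 48, so the Week 48 figures are nearest to the main analysis. True 2-year OS is 66.7 to 82.0% in these cases, so the median is not reached by then with or without the loss; what moves is the curve.

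OS is secondary and descriptive, and the primary quality-of-life endpoint and sample size are unaffected. Severity is minor, but the correction is worth making because it is cheap and lost follow-up is hard to repair.

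**What to change.** 1. **Protocol 5.4.1:** remove the no-progression condition from the survival part of the follow-up sentence, so that it agrees with 5.1, the post-treatment text of 5.3.1.1 and the footnotes to Appendices D and E.
2. **Protocol 6.1.1.1:** keep the instruction on how progression is recorded, and delete or separate the statement on discontinuation from the study. Progression alone should end neither study participation nor the 6-monthly survival calls. No rule on stopping drug belongs in this edit, and no new eCRF is needed.
3. **Protocol 5.3.1.1, Disease Assessments:** align the follow-up call sentence, for consistency only.
4. **OS table:** report the number of subjects censored at or soon after progression, for example within 60 days, so that a reader can judge any loss.
5. **SAP, as a separate minor clarification:** state that the OS rule in 10.1.2 (last contact or last known alive) governs over the cutoff-date rule in 6.4 for subjects with no recorded death.

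The cost is wording edits carried in a protocol amendment, with the usual IEC/IRB approval across about 43 sites, one SAP sentence and one count in a table. The calls themselves are already planned.

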5.4.2 Discontinuation of Entire Study

AbbVie may terminate this study prematurely, either in its entirety or at any study site, for reasonable cause provided that written notice is submitted in advance of the intended termination. The investigator may also terminate the study at his/her site for reasonable cause, after providing written notice to AbbVie in advance of the intended termination. Advance notice is not required by either party if the study is stopped due to safety concerns. If AbbVie terminates the study for safety reasons, AbbVie will immediately notify the investigator by telephone and subsequently provide written instructions for study termination.

